Data analysis	
The Full Analysis Set (FAS) comprises all subjects who receive at least one dose of study treatment (eltrombopag). The FAS will be the primary population in the assessment of efficacy.
		

	
The Safety set is identical as the Full Analysis set in the study. All safety analyses will be done using the Safety Set.
 
The primary analyses will be performed when all the subjects have completed the Week 26 visit or discontinued earlier.
 
The primary endpoint is the hematologic response rate at Week 26, which is defined as the proportion of all subjects who meet any of the IWG criteria listed above. The proportion of the hematological response will be summarized using point estimates and 90% exact (Clopper-Pearson) confidence intervals (CI). The distribution function of time to hematologic response will be estimated using the Kaplan- Meier method. The median time to hematologic response along with 90% CIs will be presented. If a subject has no response or withdraw from the study before or at the cutoff date, this subject will be treated as censored at the maximum follow up of the entire trial.
 
For the rest of the efficacy and safety endpoints (i.e. AE, vital sign, laboratory assessment), summary statistics will be presented using n, mean, standard deviation, median, 25th and 75th percentiles, minimum and maximum for continuous data and frequencies and percentages for categorical data. Shift and abnormality tables will be provided for each laboratory and vital sign assessment.
 
Eltrombopag plasma concentration data will be listed and summarized by dose, visit and time point, and listed by subject, visit and time point. Descriptive statistics will consist of arithmetic and geometric mean, median, standard deviation, arithmetic coefficient of variation (CV), geometric CV, minimum and maximum. Zero concentrations will not be included in the geometric mean calculation.
 
Where possible, PK parameters will be determined by applying non-compartmental method(s) using Phoenix WinNonlin version 6.4 or above (Pharsight, Mountain View, CA). Derived PK parameters, including but not limited to: time to peak concentration (Tmax), maximum plasma concentration following drug administration (Cmax), area under the plasma concentration-time curve over the dosing interval on multiple dosing (AUCtau), area under the plasma concentration-time curve from zero (pre-dose) to the last quantifiable sample time (AUClast), will be summarized with the descriptive statistics, arithmetic and geometric mean, median, standard deviation, arithmetic CV, geometric CV, minimum and maximum. Only median values and ranges will be given for Tmax. Missing data will not be imputed.

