## **8 Visit schedule and assessments**

The Assessment Schedule lists all of the assessments when they are performed. All data obtained from these assessments must be supported in the subject's source documentation.

Subjects should be seen for all visits/assessments as outlined in the assessment schedule or as close to the designated day/time as possible. Missed or rescheduled visits should not lead to automatic discontinuation. Subjects who prematurely discontinue the study for any reason other than withdrawal of consent should be scheduled for a visit as soon as possible, at which time all of the assessments listed for the final visit will be performed. At this final visit, all dispensed investigational product should be reconciled, and the adverse event and concomitant medications recorded on the CRF.

Allowed visit windows are specified as follows:

- When dose modification, each visit must be completed  $\pm$  3 day until dose stabilization,
- Until stabilization of dose, each visit must be completed  $\pm$  3 day,
- After stabilization of dose, each visit must be completed  $\pm$  7 day,
- The efficacy assessment visit (week 13, 26 and 52) must be completed  $\pm$  3 day,
- The safety follow-up visit must be completed  $\pm$  7 day.

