#### **Time to hematological response**

Time to hematological response is defined as the time from the date of first study drug administration to the first hematological response which is defined in [Section 12.4.1](#). All subjects in the FAS will be included in the time to hematological response calculations. The

distribution function of time to hematologic response will be estimated using the Kaplan-Meier method and will be plotted. The median time to hematologic response along with 90% CIs will be presented. If a subject does not meet hematological response before or at the cutoff date, censoring will be performed using the maximum follow up of the entire trial.

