Clinical Development

ETB115/Eltrombopag/Revolade®

CETB115E2202 / NCT03988608

**A non-randomized, open-label, multi-center, phase II study
to assess the safety and efficacy of eltrombopag in
Chinese subjects with refractory or relapsed severe
aplastic anemia**

**Statistical Analysis Plan (SAP)
Final Analysis**

Author: Trial Statistician, [REDACTED]

Document type: SAP Documentation

Document status: Final 1.0

Release date: 22-Mar-2023

Number of pages: 36

Document History – Changes compared to previous final version of SAP

Date	Time point	Section	Changes
06-Dec-2019	Prior to FPFV		N/A - First version
19-Aug-2021	Prior to DBL of Primary analysis	Section 2.3.1	In light of COVID-19 pandemic, additional analysis of protocol deviations related to COVID-19 pandemic were added.
		Section 2.5.1	Add a note to clarify 'No platelet/RBC transfusion requirement for 8 weeks'.
		Section 2.5.4	Add supplementary analyses for primary endpoint to analyse derived hematologic response programmatically.
		Section 2.7.1	To clarify time to response and duration of response should be analyzed and plotted for four assessment criteria.
		Section 2.7.1	For duration of response, give a definition for relapse.
		Section 2.7.1	For summary of shift baseline for platelet transfusion independence and RBC transfusion independence, give definition for Platelet and RBC transfusion independence.
		Section 2.7.2	Plots of Median and interquartile range were added for platelet count, hemoglobin and neutrophil count.
		Section 2.8.4.1	Add normal range for ECG findings.
		Section 2.12	Remove analysis for time to clonal evolution due to limited events of clonal evolution.
09-Feb-2022	Prior to DBL of updated analysis	General	Add some sentence to make it clear for which analysis will not be reproduced at updated analysis and final analysis.
		Section 2.3.5	Add a few more categories for patients disposition
		Section 2.7.1	Add a summary analysis for relapse-free probability in duration of response.
			Add a summary analysis for proportion of subjects with 50% transfusion reduction.
22-Mar-2023	Prior to DBL of final analysis	General	Add some sentence to make it clear for which analysis will not be reproduced at final analysis.
		Section 5.3	Clarify the rules to derive Reticulocyte absolute count which are missing.

Table of contents

Table of contents	3
1 Introduction	8
1.1 Study design.....	8
1.2 Study objectives and endpoints	9
2 Statistical methods.....	10

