2.7.1 Secondary endpoints

The following analyses Changes in platelet count, hemoglobin and neutrophil count, Duration of hematological response, Maximum duration of Platelet and RBC transfusion independence will be generated for the final CSR.

Hematological Response at Week 13 and Week 52

Hematologic response rate at Week 13 and Week 52 will also be assessed by investigator according to the International Working Group (IWG) criteria for the primary endpoints shown in the [Table 2-2](#) above.

The analysis for hematologic response rate at Week 13 will only be produced at primary analysis, and hematologic response rate at week 52 will only be produced at updated analysis.

Changes in platelet count, hemoglobin and neutrophil count

Value and changes in platelet count (in the absence of platelet transfusion), hemoglobin (in the absence of RBC transfusion) and neutrophil count (in the absence of G-CSF) will be calculated according to the lab test results entered into CRF.

Time to hematological response

Time to hematological response is defined as the time from the date of first study drug administration to the first hematological response which is defined in [Section 2.5.1](#). All subjects in the FAS will be included in the time to hematological response calculations.

These will be analyzed and plotted for four assessment criteria: Hematological Response; Platelet/Platelet Transfusion; Hemoglobin/RBC Transfusion; Neutrophils.

The analysis for time to hematological response will only be produced at primary analysis.

Duration of hematological response

For subjects who responded, duration of hematological response will be defined as the number of months from the first date of a hematological response which is defined in [Section 2.5.1](#) until the first date of a relapse (defined as not meeting the response criteria) or a death. Only subjects with at least 2 response assessments are included in the duration of response assessment. Patient still responding at the cut-off date will be censored at date of last response assessment.

These will be analyzed and plotted for four assessment criteria: Hematological Response; Platelet/Platelet Transfusion; Hemoglobin/RBC Transfusion; Neutrophils.

Frequency and amount of transfusion

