2.7.2 Statistical hypothesis, model, and method of analysis

Hematological Response at Week 13 and Week 52

The number and percentage of subjects who meet the hematological response criteria (at Week 13 and Week 52 respectively) will be presented and exact 90% confidence interval will be reported. And the number and percentage of assessment item for the hematological response criteria and for the detailed hematological response criteria will be presented.

The derived response by programming at week 13 and Week 52 will also be summarized as above.

Changes in platelet count, hemoglobin and neutrophil count

Values and changes in platelet count (in the absence of platelet transfusion), hemoglobin (in the absence of RBC transfusion) and neutrophil count (in the absence of G-CSF) will be summarized at each visit. Descriptive statistics including mean, SD, median, 25th and 75th percentiles, minimum, and maximum will be summarized for the changes.

Median and interquartile range will be plotted.

Time to hematological response

The distribution function of time to hematologic response will be estimated using the Kaplan-Meier method and will be plotted. The median time to hematologic response along with 90% CIs will be presented. If a subject does not meet hematological response before or at the cutoff date, censoring will be performed using the date of the last assessment.

Duration of hematological response

The distribution function of duration of hematologic response will be estimated using the Kaplan-Meier method and will be plotted. If the number of relapses or deaths allows, the median time to hematologic response along with 90% CIs will be presented.

Relapse-free probability will be estimated using the Kaplan-Meier method at 3 months, 6 months, 9 monthes, one year, and yearly after as well.

Frequency and amount of transfusion

The frequency and the amount of platelets transfusion in each period (Baseline: 4 weeks before Day 1; Week 13, 26, 52: 4 weeks before each visit day) will be summarized by descriptive statistics including mean, SD, median, 25th and 75th percentiles, minimum, and maximum.

Proportion of subjects with transfusion decrease

The number and percentage of subjects with platelet or RBC transfusion decrease or transfusion-free in each period will be presented.

In addition, the number and percentage of subjects with 50% platelet or RBC transfusion reduction in each period will be presented.

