2.7.3 Handling of missing values/censoring/discontinuations

Hematological Response at Week 13 and Week 52

For the analysis of hematological response at Week 52, patients who are still ongoing but have not reached the considered timepoint yet will not be included in the analysis of response at that timepoint. However, patients with a missing or 'Non-evaluable' response for other reasons will be treated as non-responders at that timepoint in the calculation of the hematological response rate.

Time to hematological response

For time to hematological response, if a subject does not meet hematological response before or at the cutoff date, censoring will be performed using the date of the last assessment.

Duration of hematological response

For duration of hematological response, patient still responding at the cut-off date will be censored at date of last response assessment.

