3.1 Primary analysis

The hematologic response rate at Week 24 in the pivotal study of NIH-09-H-0154 was 40%. Assuming a same response rate (40%) in Chinese subjects, the 90% confidence interval of the hematological response rate with a total of 20 subjects will be (21.7%, 60.6%).

Below table shows the 90% CIs for various observed response rate. The maximum half-width of the 90% CIs is 19.8%.

Table 3-1 90% CIs for various observed response rate

Sample size	# of responders	Hematologic response rate (%)	90% CI (%)
20	4	20	(7.1, 40.1)
20	6	30	(14.0, 50.8)
20	8	40	(21.7, 60.6)

Sample size	# of responders	Hematologic response rate (%)	90% CI (%)
20	10	50	(30.2, 69.8)

The 12 evaluable subjects for intensive PK sampling was chosen based on feasibility and practical considerationzs to assist in characterizing the PK of eltrombopag in Chinese subjects.

4 Change to protocol specified analyses

No change from protocol specified analysis was made.

5 Appendix

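### Time to response: the SAP replaces the protocol's censoring rule with an undefined date, does not declare the change, and can report more responders on the curve than were observed

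*SAP*

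**What the plan says.** The protocol gives one rule in two places. Section 12.5.1 says that for a subject without response by the cutoff "censoring will be performed using the maximum follow up of the entire trial". The data analysis part of the protocol summary covers both non-response and withdrawal, and says "this subject will be treated as censored at the maximum follow up of the entire trial".

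The SAP gives a different rule, also twice. Section 2.7.2 says "censoring will be performed using the date of the last assessment", and Section 2.7.3 repeats it: "if a subject does not meet hematological response before or at the cutoff date, censoring will be performed using the date of the last assessment". Neither place says which assessment is meant. For duration of response, SAP 2.7.1 and 2.7.3 do name the response assessment.

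SAP Section 4 reads "No change from protocol specified analysis was made". The document history has one entry on the analysis of time to response, "To clarify time to response and duration of response should be analyzed and plotted for four assessment criteria", and it does not concern censoring. SAP 2.7.1 adds: "The analysis for time to hematological response will only be produced at primary analysis".

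**The concern.** The protocol rule uses one trial-wide value and the SAP rule a separate date for each subject, so they are different derivations. The protocol rule keeps every subject without response in the risk set past the last response, and 1-KM then ends at responders divided by N. The SAP rule removes such a subject at the last assessment, and Kaplan-Meier treats the subject as though a response might have followed at the same rate as in those who remain. That is hard to defend for someone who died or stopped without response. It also sits badly with the primary endpoint, where SAP 2.5.3 counts those who discontinue before Week 26 as non-responders.

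Time to response is a named secondary endpoint. All FAS subjects enter it, a median with 90% CI is planned, and four curves are to be plotted (overall and three lineages). The SAP rule can print a median time to response when fewer than half the subjects responded.

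**Working it through.** **Inputs from the documents.** N = 20 and a 40% response rate, so 8 responders and 12 non-responders (Protocol 12.8.1, SAP 3.1). Response is assessed at Weeks 13 and 26. On visit windows, Protocol 8 says "The efficacy assessment visit (week 13, 26 and 52) must be completed" within 3 days either way. Protocol 3 has subjects without response at 6 months stop the drug, with a follow-up visit 30 days after stopping.

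**Assumed, because the documents do not give them.** Three responses at Week 13 and five at Week 26; the number of early dropouts (0 to 6, all non-responders); the spread of visit days.

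**The plan's own figure.** The exact 90% Clopper-Pearson interval for 8/20 recomputes to (21.7%, 60.6%), as stated. The largest half-width in the table, at 10/20, recomputes to 19.8 percentage points. The plan gives no figure for time to response.

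**Protocol rule.** No non-responder leaves before the last response, so 1-KM = 1 - (17/20)(12/17) = 1 - 12/20 = 40.0%. The median is not reached, whatever the dropout.

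**SAP rule (a): early dropout.** Let a non-responders leave before Week 13 and b between Weeks 13 and 26, with the others censored no earlier than the last response. Then 1-KM = 1 - (1 - 3/(20 - a))(1 - 5/(17 - a - b)).

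| a, b | Calculation | 1-KM | Median reported |
|---|---|---|---|
| 0, 0 | 1 - (17/20)(12/17) | 40.0% | no |
| 1, 1 | 1 - (16/19)(10/15) | 43.9% | no |
| 2, 2 | 1 - (15/18)(8/13) | 48.7% | no |
| 3, 2 | 1 - (14/17)(7/12) | 52.0% | yes |
| 3, 3 | 1 - (14/17)(6/11) | 55.1% | yes |

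With responses split 4 and 4 instead, 2, 4, 5 and 6 dropouts (1+1, 2+2, 2+3 and 3+3) give 43.6%, 48.1%, 50.5% and 54.1%.

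**SAP rule (b): no dropout, censoring on the subject's own Week 26 date.** If m of the 12 non-responders are seen at least a day before the five late responders, 1-KM = 1 - (17/20)(1 - 5/(17 - m)).

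- m = 0: 40.0%
- m = 4: 1 - 0.85 × 8/13 = 47.7%
- m = 6: 1 - 0.85 × 6/11 = 53.6%, and a median is reported

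Visit days were also simulated, with no dropouts and events placed before censorings at ties:

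| Visit days | Mean 1-KM | Median reported |
|---|---|---|
| Uniform within 3 days of target | 64% (5th to 95th percentile 46% to 100%) | about 85% of trials |
| Uniform within 1 day of target | 55% | 69% of trials |

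For the 3-day spread, response splits of 4/4 and 2/6 give means of 61% and 67%.

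**SAP rule (c): no dropout, censoring at the 30-day follow-up visit.** Every non-responder is censored after the last Week 26 response, so 1-KM = 40.0%, the same as the protocol rule.

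The SAP rule is therefore never below the observed proportion. When nobody drops out, the reading given to the last assessment alone decides whether the two documents agree.

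**The case against.** The strongest reply concerns size. The large simulated values require the last assessment to be the last response assessment. The SAP writes exactly that for duration of response and does not write it here, so the plainer reading may be any last visit, which is case (c) with no difference. The visit window is a tolerance and not a distribution. If 80% of visits fall on the target day and the rest are uniform within 3 days, the 50th percentile of 1-KM is 43% and a median is reported in 36% of trials. If 80% of non-responders have their follow-up visit before the cutoff, the mean is 42% and a median is reported in 0.2%. In case (a), a median needs 5 or 6 of 20 subjects to leave early. All of this stands, and the simulated figures should be read as one case under one reading.

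Two further points stand in part. The document history lists changes between SAP versions, so a rule present in the first version would not appear there; the case for an undeclared change rests on Section 4. Censoring at last assessment is also a familiar convention, and the protocol rule taken literally credits subjects still on study with follow-up nobody observed. Neither point reconciles the two documents or makes Section 4 correct.

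Finally, the study is single-arm and estimates without testing, and the observed response rates with exact intervals are reported elsewhere. That limits the harm. It does not justify a median that most subjects did not reach.

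**Conclusion.** The concern holds. The two documents prescribe different censoring for the same secondary endpoint, Section 4 is wrong to declare no change, and the SAP's censoring date is undefined. With 8 of 20 responding, the protocol rule always ends at 40.0% with no median. The SAP rule ends anywhere from 40.0% upward: 43.9% to 55.1% with 2 to 6 early dropouts, and 47.7% or 53.6% without dropout if 4 or 6 non-responders happen to be seen first and are censored on their Week 26 date. These values rest on assumed response timing, dropout and visit spread; that the SAP curve can exceed the observed proportion does not. The primary response rate and its interval are untouched and the analysis is descriptive, so this should be fixed but does not threaten the main result.

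**What to change.** In SAP 2.7.2 and 2.7.3:

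- Keep subjects who die or discontinue without response in the risk set to the maximum follow-up, as the protocol does, and say how that maximum is determined at the primary cutoff. Alternatively, report cumulative incidence with death or discontinuation without response as a competing event.
- State separately how subjects still on study without response in a given lineage are censored, since the literal protocol rule would give them unobserved follow-up.
- Define the last assessment: which type of assessment, and what applies to a subject with none after baseline.

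Declare any remaining difference from the protocol in Section 4.

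This output is produced only at the primary analysis, so a SAP edit alone changes nothing already reported. Re-run or supplement the four curves and print the observed proportion of responders beside each.

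The cost is SAP wording, a small change in derivation and four replacement or supplementary outputs. A reported median may become not reached.

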2.7.3 Handling of missing values/censoring/discontinuations

Hematological Response at Week 13 and Week 52

For the analysis of hematological response at Week 52, patients who are still ongoing but have not reached the considered timepoint yet will not be included in the analysis of response at that timepoint. However, patients with a missing or 'Non-evaluable' response for other reasons will be treated as non-responders at that timepoint in the calculation of the hematological response rate.

Time to hematological response

For time to hematological response, if a subject does not meet hematological response before or at the cutoff date, censoring will be performed using the date of the last assessment.

Duration of hematological response

For duration of hematological response, patient still responding at the cut-off date will be censored at date of last response assessment.

2.8 Safety analyses

All safety analyses will be based on the safety set.

The safety summary tables will include on-treatment assessments collected no later than 30 days after last dose of study treatment (see definition in [Section 2.1.1](#)).

All safety assessments will be listed by patient and flagged appropriately.

All safety assessments will be generated for the final CSR except for subgroup of interest.

2.8.1 Adverse events (AEs)

Coding and grading

Adverse events will be coded using the Medical dictionary for regulatory activities (MedDRA) Terminology and their severity assessed according to the Common Terminology Criteria for Adverse Events (CTCAE) version 4.03.

General rules for AE Reporting

AE summaries will include all AEs occurring during on treatment period. All AEs collected in the AE (e)CRF page will be listed along with the information collected on those AEs e.g. AE

relationship to study drug, AE outcome etc. AEs with start date outside of on-treatment period will be flagged in the listings.

AEs will be summarized by number and percentage of subjects having at least one AE, having at least one AE in each primary system organ class (SOC) and for each preferred term (PT) using MedDRA coding. A subject with multiple occurrences of an AE will be counted only once in the respective AE category. A subject with multiple CTCAE grades for the same preferred term will be summarized under the maximum CTCAE grade recorded for the event. AE with missing CTCAE grade will be included in the 'All grades' column of the summary tables.

In AE summaries, the primary system organ class will be presented alphabetically and the preferred terms will be sorted within primary SOC in descending frequency. The sort order for the preferred term will be based on their frequency.

The following adverse event summaries will be produced for AEs occurring during the on-treatment period; overview of adverse events and deaths, AEs by SOC and PT, summarized by maximum CTCAE grade, summarized by relationship (all AEs and AEs related to study treatment), seriousness (SAEs and non-SAEs), leading to treatment discontinuation, leading to dose interruption/changes, requiring additional therapy and leading to fatal outcome.

Furthermore, AE occurring during the on-treatment period will be summarized by subgroup defined by age group (<65 years and \geq 65 years), gender (male and female) and concomitant use of CsA and anabolic steroids at baseline (Yes and No) (see [Section 2.2.1](#)). These summaries include: AEs by SOC and PT, AEs with suspected relationship to study drug by SOC and PT and SAEs by SOC and PT. These subgroup analysis will not be reproduced for final CSR.

In addition, on treatment adverse events will be summarized by SOC and PT and by periods (by \leq 30 days, $>$ 30 to \leq 90 days, $>$ 90 to \leq 180 days, $>$ 180 to \leq 270 days, $>$ 270 to \leq 360 days, and $>$ 360 days). Time of onset of first episode will be used when experiencing the same episode in a subject.

